Appendix A: Example Study Flowchart

Appendix B: Safety Reporting Fax Cover Sheet

Appendix C: UEFI

Appendix D: SDMT

Appendix E: Jamar handheld dynamometer

Appendix F: 9-Hole Peg Test

Appendix G: Fatigue Severity Scale (FSS)

Appendix H: MUSIQoL

1. INTRODUCTION

Multiple sclerosis (MS) is a chronic demyelinating disease of the central nervous system (CNS) that affects approximately 2.5 million people worldwide. It is a chronic condition characterized clinically by focal disorders of the optic nerves, brain and spinal cord, which remit to a varying extent and recur over a period of many years. Most patients eventually experience progression and accumulation of symptoms which can include profound muscle weakness, impaired gait and mobility, bladder and bowel dysfunction, cognitive and visual impairments and sexual dysfunction [1].

In patients that have disability that involves the upper extremity, this can lead to loss of independence in activities of daily living such as dressing, feeding and hygiene [2]. Upper extremity(UE) strength is also important for a patient being able to independently shift weight in a wheelchair, maneuver an electric wheelchair, and change position in bed, thus minimizing risk for decubitus ulcers. As opposed to lower extremity function, a very small loss of strength and function can translate into significant changes in functional independence. The loss of independence then impacts quality of life (QoL) for both the patient and the caregiver(s).

2. OBJECTIVES

2.1 PRIMARY OBJECTIVES

To measure for clinical stabilization (defined as no significant change (≤20%) from baseline of UE function in multiple sclerosis patients with upper extremity impairment treated with Ocrevus[™].

2.2 SECONDARY OBJECTIVES

To evaluate the relationship between UE function (objective and subjective) and fatigue, cognition and QoL.

3. STUDY DESIGN

3.1 DESCRIPTION OF THE STUDY

Ocrevus[™] is the first FDA approved disease-modifying treatment for primary progressive MS as well as relapsing MS [3]. In the clinical trials considered by the FDA (OPERA I/II, ORATORIO), the highest Expanded Disability Status Scale (EDSS) included in the participants was 5.5 (OPERA I/II) and 6.5 (ORATORIO) [4]. The EDSS score is heavily weighted on walking ability and is not a useful measurement for UE function [5,6]. The primary endpoint in the primary progressive MS trial with Ocrevus[™] was EDSS and in the relapsing MS studies, EDSS was used as a secondary endpoint. The Multiple Sclerosis Functional Composite (MSFC) score (Z score), a composite of quantitative measure of walking speed, upper limb coordinated movement (9 Hole Peg Test/9HPT) and cognitive function, was obtained as a secondary clinical

measure with scores being favorably higher in patients treated with Ocrevus[™] (OPERA I/II). The z score, however, is not very useful in delineating which of the three clinical functions was maintained or showed less progression given that three domains are included in the score [7,8,9]. Data presented recently from the Oratorio trial analyzed the intention to treat population of PPMS patients and the subgroups of patients with upper extremity functional impairment using the 9HPT; results demonstrated reduction in risk of clinical progression in upper extremity disability in patients treated with Ocrevus compared to placebo. There was improvement in the change from baseline to week 120 in 9HPT time in treated patients. Abnormal baseline 9HPT was defined as >25 seconds and upper extremities were defined as "better hand" and "worse hand", each individually tested, with clinical progression determined at 12 and 24 weeks in 3 sub-categories of progression: lengthened time of 9HPT >15%, >20% and 25%. [10]

In our study we aim to not only replicate the results in the Oratorio trial with upper extremity dysfunction, but also widen the spectrum of patients that may benefit (given an expanded MS population of patients, not exclusive to PPMS and widen the range of potential disability that the patients may have (broader EDSS rage 4-8). We anticipate that by using a test that better emulates activities of daily life performed with the upper extremity, such as the TEMPA (Test d'Evaluation de la performance des membres Superieurs e Personnes Agees) we will obtain more real life application of the benefits of receiving treatment with Ocrevus, and anticipate that patients can maintain the function they have or potentially improve function.

3.2 RATIONALE FOR STUDY DESIGN

We anticipate the use of Ocrevus[™] in patients with progressive disease which includes those with advanced disability, regardless of a dearth of data to guide the prescriber regarding its effect in this population. The rational for this study is to gain information which will help the prescribers of Ocrevus[™] answer the question "Will Ocrevus[™] help me if I have hand or arm weakness?" especially if posed by a more advanced MS patient (EDSS 4.0-8.0 with UE involvement) than those included in the clinical trials. In previous trials (ORATORIO), the included patients were only those diagnosed with primary progressive MS and their entry EDSS was of a lower disability range (3.0-6.5) than those proposed in this study. Therefore, the results cannot be completely extrapolated to the population of multiple sclerosis patients with more advanced disability that we propose to study. We aim to identify MS patients that have weakness in at least one upper limb, knowing that delaying disability affecting the functional use of the UE will help patients remain independent for some activities of daily life and will contribute to an improved quality of life.

The importance of choosing validated upper limb outcome assessment tools cannot be emphasized enough. The Nine-Hole Peg Test (9HPT), an objective measure of manual dexterity, which is incorporated into the MSFC, is a widely used measure across most clinical trials in multiple sclerosis populations.

The EDSS is an ordinal scale of neurological disability designed specifically for MS patients and will provide specific quantitative measure of upper limb strength, sensory impairment and ataxia of the upper limb with each Functional System Subscore. This score will aid in deciphering limitations due to tremors or ataxias.

The Test d'Evaluation de la performance des Membres Supérieurs des Personnes Agées (TEMPA) has been previously studied for validity in clinical trials and specifically in multiple sclerosis patient populations and there was a strong correlation between the TEMPA and 9HPT. [11, 12] The TEMPA consists of 9 tasks that mimic tasks of daily living such as picking up a jar, pouring water from a pitcher, handling coins, writing on an envelope and opening a pill container, as examples. The tasks are assessed by a rater by measuring speed of execution (seconds) and by functional rating of the subject's independence in performing them using an ordinal scale of 0 (completed without difficulty) to -3 (could not complete the task). The test provides a unilateral and bilateral score and evaluates different grasp, grip and pinch functions. Obtaining baseline scores and sequential measurements will allow us to graph scores over time for each patient and assess the change. This type of testing would give us a clear picture of any changes in UE functionality and would highlight meaningful clinical data that would be easily translated to patients- stability of function vs clinical progression >20% change from baseline. This key data would be a helpful reference when discussing starting treatment with Ocrevus™ in this population of patients.

The normative values available for the TEMPA were obtained in the elderly (ages 60-80, men and women). The speed of execution of the 9 tasks in each hand takes about 70 to 80 seconds to complete in this population. [12] When one reviews the validity study of the TEMPA in MS patients [average EDSS was 7 and age median was 46 years old], this same parameter took them between 100 and 400 seconds [1 and 1/2 to 6 minutes] to complete.

Schwid et al in 2002 showed that MS patients did not vary from their baselines in performing the 9HPT by >20% day-to day and therefore the if there was change measured >20% from their baseline this was stipulated to indicate change in function [13].

In a pilot study where a technology enhanced training program for improving upper limb muscle strength in MS patients the TEMPA was used at baseline and 8 weeks later, and there was a trend towards statistical significance of improvement in function with TEMPA change of 20 to 40 seconds [14]. Since the 9HPT and TEMPA have been show to correlate and there are numerical values measured in both, we plan to emulate the Oratorio study and look at >15%, >20% and >25% [in better hand and in worse hand] change from baseline with increases in time implying clinical progression and stability or decrease in time implying stability or improvement in function.

The Jamar dynamometer is validated tool often used by occupational therapist to measure grip strength [15]. Grip strength is an important part of daily living tasks and can give clinicians insight into patient restrictions and clinical changes.

The Upper Extremity Functional Index (UEFI) is a self-report questionnaire that has been found reliable, valid and sensitive as a patient- reported outcome measure tool for quantifying UE function rated on a 5-point Likert scale This 20item measure is recommended in research and clinical setting due to its unidimensionality: it measures only UE function [16,17]. Scores range from 0 to 60 with lower scores indicating more functional difficulty. It has been used in several studies in patients with musculoskeletal upper extremity problems, to include patients with MS, and UEFI scores correlated with mean 9-HPT scores. [18] We anticipate that patients in our study will have perceived stabilization of their upper extremity function and plan to use the UEFI to measure this by means of its validated 9 points of change from baseline for minimal detectable change in function.

The Symbol Digit Modalities Test (SDMT) is a validated measure used to assess mental processing speed in MS clinical trials and has an oral response version. There is evidence that cognitive measures may correlate with upper extremity function. This can possibly be explained by a cerebral relationship between motor function and cognition [19]. As a secondary measure we will collect SDMTs at each visit to explore correlations with upper extremity function, as well as QoL measures.

The natural history of progression of disability in MS is foreseeable in a 2-year span period and this is evident when one examines the placebo population in the recent Oratorio trial; obtaining these measures over a 2-year period aims to observe stability of the upper limb function with Ocrevus[™] treatment.

3.3 OUTCOME MEASURES

- The UE function will be assessed every 6 months over 24 months to gauge for any small changes at certain intervals but to also have a sufficient length of time that can be compared in order to assess for any type of change over time. *
- Incidence of UE functional changes (improved, worsening or stable) with scores of time and performance on the TEMPA.
- In this group of patients (advanced disability) there is less concern with relapse rate reduction; relapses happen at a low rate. There is more concern regarding any loss of function, and we will focus on UE function. Studies like this would provide better data for this type of patient aiding in the process of selecting appropriate disease modifying therapy.

*UE function includes measures on the TEMPA, UEFI and 9HPT.

UEFI is subjective and answered by the patient. The Upper Extremity Functional Index (UEFI) is a self-administered questionnaire which measures disability in patients with upper extremity conditions. The questionnaire lists 20 activities and the patient gives a score to each based on the difficulty they have completing that activity. The scores given to the 20 questions are added to give a highest possible score of 80. The lowest possible score is 0. A lower score indicates that the person is reporting increased difficulty with the activities as a result of their upper limb condition. The change from baseline per patient and for group means will be analyzed. A clinically significant change is determined as a 12% change. [20]

The TEMPA scale is composed of nine standardized tasks which represents activities of daily living. Four items are unilateral (pick up and move a jar; pick up a pitcher and pour water into a glass; handle coins; pick up and move small objects) and five bilateral tasks (open a jar and take a spoonful of coffee; unlock a lock and open a pill container; write on an envelope and stick on a stamp; shuffle and deal playing cards; put a scarf around one 's neck). The outcome parameters used in this study are speed of execution (seconds) and the functional rating. The functional rating refers to the participant's independence in each task measured on a four-level scale: (0) successfully completed without hesitation or difficulty; (-1) completed, but with some difficulty; (-2) partially executed or some steps were performed with significant difficulty; and (-3) not completed, even if any degree of assistance was offered. A total score will be determined by adding the scores obtained for both the unilateral and bilateral tasks. Individual analysis of the unilateral and bilateral scores will be conducted to evaluate for functional improvement in the affected UE. Scores typically range from 0 to -50, with higher scores representing better performance. [12] The UE function will be measured by a consistent rater that is trained and qualified (must be a MD or equivalent).

The 9HPT is an objective measure of manual dexterity, which is incorporated into the MSFC, is a widely used measure across most clinical trials in multiple sclerosis populations. The time to completion is measured twice on both the dominant and non-dominant hand. For this study purpose will also record the "better" and "worse" limb so that the data can be cautiously compared to prior studies completed in multiple sclerosis patients. The task of the 9HPT is for the patient to pick up each individual peg, one at a time, and place it in the board (that has the same number of peg holes for each peg). Once all the pegs are placed in the peg holes the patient then removes each peg, again one at a time, placing them back into the peg bowl from which they were originally located. Although this measure has been used in several multiple sclerosis trials due to its ease of administration, there are many other factors of upper extremity function that are not being assessed that can be captured by the TEMPA.

3.3.1 Primary Outcome Measure

No significant change in UE function over 24 months after initiation of Ocrevus™ measured objectively by measure of time to completion (seconds) and functional

scores on TEMPA (0 to -3). The hypothesis is that there is (stabilization) no significant change (within 20%) of TEMPA score from baseline to 24 months

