4.9.6 Determination of Sample Size

It is expected that 30 patients will be eligible to enter this study during the proposed timeframe. This is a pilot study; the TEMPA is a more comprehensive assessment of upper extremity function which we will use in the analysis of this group of patients to evaluate what percentage remain stable (within 20% variation from baseline) and analyze correlations with other measures of upper extremity function (9HPT and patient perception using the UEFI). Therefore, this is not a calculated sample size as there is a lack of historical data available for this population and the modalities of testing we plan to utilize. We do not have historical data to gather estimates for an accurate power calculation. We plan to gather data on 30 patients but will screen up to 35 in case of screen failures or early withdrawals. Even with the limited calculations we believe that we will be able to analyze for a clinically meaningful lack of change (stabilization).

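### The primary hypothesis and the percentage stable rest on two TEMPA measures under one 20% threshold, with no rule for which decides or how a patient stable on only one is classed

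*Combined protocol and SAP*

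**What the plan says.** - **Measures (3.3).** On TEMPA: "The outcome parameters used in this study are speed of execution (seconds) and the functional rating". Each task is rated from 0 (best) to -3, and the ratings are added to a functional total. No composite of that total with time is described. The same section lists as an outcome: "Incidence of UE functional changes (improved, worsening or stable) with scores of time and performance on the TEMPA".
- **Primary outcome (3.3.1).** Stability is "measured objectively by measure of time to completion (seconds) and functional" scores. The hypothesis follows in the singular: "The hypothesis is that there is (stabilization) no significant change (within 20%) of TEMPA score from baseline to 24 months".
- **Analysis (4.9.3).** The primary endpoint is TEMPA scores at 24 months against baseline by paired t-test, with a repeated-measures ANCOVA across visits. Neither names the measure. A change above 20% of baseline is the clinical threshold, and the data are analysed both in seconds and as functional scores. A further review uses cut-offs of 15%, 20% and 25% in the better and the worse hand, with a direction given for time only.
- **Sample size (4.9.6).** Thirty patients, not calculated. The analysis is "to evaluate what percentage remain stable (within 20% variation from baseline"), with no measure named.

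**The concern.** The plan names two measures but has one hypothesis, one threshold and one percentage. It does not rank the measures, require both, or say what to do when they disagree. Two analysts following it faithfully could report different percentages from the same 30 patients.

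This matters because the aim is to show absence of change in a single treated group. With no control arm and no power calculation, readers will look to the percentage stable, which section 3.2 intends as reference data when treatment is discussed with such patients. If the deciding measure is fixed only after the data are known, readers cannot tell whether the definition was chosen for its result.

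**Working it through.** The plan states no figure to reproduce: no expected percentage stable, SD, alpha or power.

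**1. The 20% rule applied to each scale**

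Inputs: threshold above 20% of baseline (4.9.3); TEMPA times of 100 to 400 s in MS patients (3.2); functional total with 0 as its best value (3.3). Percent change = |follow-up - baseline| / |baseline|.

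- Time, 200 to 230 s: 30/200 = 15%, so stable.
- Function, -4 to -5: 1/4 = 25%, so not stable. One patient could show both.
- The reverse is also possible. Time 200 to 250 s: 50/200 = 25%, not stable. Function -10 to -12: 2/10 = 20%, stable.
- One functional point as a share of baseline: 100% at -1, 50% at -2, 33% at -3, 25% at -4, 20% at -5. At baselines of -1 to -4 any one-point change breaches the threshold; from -5 a one-point change is tolerated.
- At a functional baseline of 0 the denominator is 0 and the percent change is undefined.
- On time, the rule tolerates 0.20 × 100 = 20 s to 0.20 × 400 = 80 s.

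The same percentage is therefore very strict on function in mildly affected patients, and has no value in a patient with a perfect score.

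**2. How far the headline can move**

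Assumptions, none from the plan: each measure classes a proportion p of patients as stable, with p = 0.80 or 0.85; the two classifications follow a bivariate normal with latent correlation r from 0 to 0.9; n = 30.

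With z = Φ⁻¹(p), P(both) = Φ₂(z, z; r). The gap against one measure alone is p - P(both). Expected discordant patients = 30 × 2 × [p - P(both)].

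| p | r | Stable on both | Gap (points) | Discordant of 30 |
|---|---|---|---|---|
| 0.80 | 0 | 64.0% | 16.0 | 9.6 |
| 0.80 | 0.5 | 68.7% | 11.3 | 6.8 |
| 0.80 | 0.9 | 75.0% | 5.0 | 3.0 |
| 0.85 | 0 | 72.3% | 12.8 | 7.7 |
| 0.85 | 0.5 | 75.8% | 9.2 | 5.5 |
| 0.85 | 0.9 | 80.8% | 4.2 | 2.5 |

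First row: 0.80 × 0.80 = 0.64; 0.80 - 0.64 = 0.16; 30 × 2 × 0.16 = 9.6. Last row: 0.85 - 0.808 = 0.042; 30 × 2 × 0.042 = 2.5.

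The choice between one measure alone and both moves the headline by about 4 to 16 points, or 0.042 × 30 = 1.2 to 0.16 × 30 = 4.8 patients.

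**The case against.** The best defence is that the text leans one way. The word joining the two measures in 3.3.1 suggests that both must be stable. Alternatively, the 20% threshold comes from a timed test (the 9HPT), and 4.9.3 gives a direction of progression only for time, which points to time. Each reading is reasonable, but they differ, and neither is stated as the primary definition. The time-based review in 4.9.3 also brings three cut-offs and two hands. Reading the hypothesis as the functional total alone conflicts with the words just before it, which include seconds.

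It can also be said that the percentage stable appears in the sample-size rationale of a pilot, beside a paired t-test and an ANCOVA, and that both scales may simply be reported. That stands in part: the percentage is one of several primary summaries. But the t-test names no measure either, and reporting both scales does not say which answers the single hypothesis.

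Some stronger readings are tempting but not supported:

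- A reader might count a patient as stable if stable on either measure, which greatly widens the spread. At 85% each and correlations of 0.7 down to 0, that gives 92-98%, against 78-72% for both. No passage supports an either-one rule, and zero correlation is unlikely for two measures taken from the same tasks.
- A reader might infer that a partly executed task takes less time, so that time hides lost function. The plan does not say how incomplete tasks are timed, and difficulty could equally lengthen the time.
- A reader might infer intent to pick the better result, or a breached type I error rate. The documents permit a late choice but show no intent, and they state no alpha.

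**Conclusion.** The gap is real. The primary hypothesis and the percentage stable cannot be computed uniquely as written: the deciding measure is not named, the shared 20% rule can class one patient both ways, and it has no value at a functional baseline of 0. These points follow from the plan's own rule and need no assumption.

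The size does rest on assumptions. With 80-85% stable on each measure and correlations of 0 to 0.9, the headline differs by about 4 to 16 points, the low end applying if the measures agree closely. This should be fixed before analysis. It falls short of a must-fix because the study is an uncontrolled 30-patient pilot with no stated alpha or decision rule; the harm is an ambiguous headline.

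**What to change.** Before analysis, put one headline definition of a stable patient in 3.3.1 and 4.9.3, and refer to it in 4.9.6. Either option closes the gap:

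1. **Require both**, which the wording of 3.3.1 supports: total TEMPA time not more than 20% slower than baseline, and the functional total not worse by more than a prespecified number of points. The investigators should justify that number, since the documents give no basis for one, and vary it in sensitivity analyses.
2. **Name one measure primary** and the other supportive.

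Under either option:

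- State that improvement counts as not worsened. This departs from a literal two-sided reading of within 20%, so it should be written down.
- Judge function in points, which removes the problem at baselines of 0 and near 0.
- Report each measure alone and the 2×2 table of time by function as supportive.
- Name the measure to which the paired t-test and the ANCOVA apply.

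The cost is some wording and one cross-table; TEMPA is already collected at baseline and months 6, 12, 18 and 24. The headline may move either way. Requiring both lowers it against one measure alone. A points rule that tolerates a one-point fall at baselines of -1 to -4, and counting improvers as stable, would raise it against both within 20%.
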